Appendix 1 - BSW questionnaire

Benefit, Satisfaction, and Willingness to Continue (BSW) Questions

The following q	uestions are administered by the physician:	
BENEFIT: Plea	se ask the patient the following question:	
1. Have you had	any benefit from your treatment?	□ (0) No □ (1) Yes
If YES, pleas	se ask the patient the following question:	
Have you had	little benefit from your treatment or much benefit?	☐ (1) Little benefit ☐ (2) Much benefit
SATISFACTIO	N: Please ask the patient the following question:	
2. Taking all thin	gs into account, are you satisfied with your treatment?	
☐ (1) Yes	If YES , please ask the patient the following question:	
	Are you a little satisfied with your treatment or very satisfied with your treatment?	☐ (1) A little satisfied ☐ (2) Very satisfied
□ (0) No	If NO, please ask the patient the following question:	
	Are you a little dissatisfied with your treatment or very dissatisfied with your treatment?	☐ (1) A little dissatisfied ☐ (2) Very dissatisfied
WILLINGNES	S TO CONTINUE	
3. Would you be	willing to continue treatment with this medication?	
□ (1) Yes	If $\underline{\mathbf{YES}}$, please ask the patient the following question:	
	Would you be a little bit willing to continue treatment with this medication or very willing to continue treatment with this medication?	☐ (1) A little bit willing ☐ (2) Very willing
□ (0) No	If $\underline{\mathbf{NO}}$, please ask the patient the following question:	
	Would you be a little bit unwilling to continue treatment with this medication or very unwilling to continue treatment with this medication?	☐ (1) A little unwilling ☐ (2) Very unwilling

BSW

Number	Version / Date	Page	
G02-CLP-0002_US	Rev. 08 / 27July 2021	67 of 75	

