10.3.3 Other Endpoints

The following endpoints will be assessed as other endpoints for the 6-, 12-, 24- and 36-months post activation, without formal hypothesis testing and type I error control.

- Incidence of procedure or device related adverse events from 12- to 36-months post activation
- Patient Global Impression of Improvement (PGI-I) score
- Treatment Benefit, Satisfaction, and Willingness to Continue (BSW)
- Reduction in the average number of severe/large urgency related incontinence episodes
- Improvement in OAB-q (HRQL and symptoms severity).
- Changes in the following OAB symptoms as measured by voiding diary compared to baseline:
 - Reduction in the number of micturition episodes.
 - o Reduction in the number of urgency related incontinence episodes.
 - Reduction in degree of urgency prior to void on Patient Perception of Intensity of Urgency Scale (PPIUS) from 0-4.
 - Reduction in severity of incontinence episodes (amount leaked).
- Proportion of dry subjects following treatment with the RENOVA iStim System as measured by 3
 consecutive days of a patient voiding diary
- Assessment of fecal incontinence symptoms in patients suffering from mixed fecal and urine incontinence
- Patient compliance with treatment
- Duration from treatment initiation to symptoms improvement (in subset of patients who stopped treatment after completing the 12-month visit and started again when consented for the long-term follow-up).
- Device usage

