10.7 Eligibility Criteria

10.7.1 Inclusion Criteria

1. Signed written informed consent.

Number	Revision / Date	Page
G02-CLP-0002_US	Rev. 08 / 27 July 2021	32 of 75

- 2. Female aged 18 or greater (21 or greater in the US), with no plans to become pregnant during the trial; if of bearing potential, negative pregnancy test and if sexually active, using acceptable contraception.
- 3. Subject who is mentally competent with the ability to understand and comply with the requirements of the study.
- 4. Diagnosis of UUI demonstrated on a 7-consecutive days voiding diary defined as a minimum of nine (9) leaking episodes associated with urgency, with at least one episode per day for 5 days.
- 5. More than or equal to 6 months history of UUI diagnosis
- 6. Subject with inadequate response to any of the following conservative treatments (i.e. dietary restriction, fluid restriction, bladder training, behavioral modification, pelvic muscle training, biofeedback, etc.) and pharmacologic treatment.
- 7. If used, subjects should be on stable dose of antimuscarinics and/or beta-3 adrenergic agonists for at least 3 months prior to baseline and agree to remain on stable medication consumption until the 12-month follow-up visit.
- 8. If used, subjects should be on a stable dose of tricyclic antidepressants, Selective Serotonin Reuptake Inhibitors (SSRI) and Serotonin-Norepinephrine Reuptake Inhibitors (SNRI) for at least 3 months prior to baseline.
- 9. Subjects with positive tibial nerve motor or sensory response tested via physical/neurological examination.
- 10. Subjects with normal renal function defined by GFR of 50 ml/min or more
- 11. Leg circumference of no less than 20 cm and no more than 30 cm at implantation site (i.e. 5cm above the medial malleolus).
- 12. Subject agrees to attend all follow-up evaluations and is willing and capable to completely and accurately fill out voiding diaries and questionnaires and is willing to complete required exams and tests.

The following inclusion criteria will be re-evaluated for patients who completed 12-months follow-up and exited the study:

1. Subject who is mentally competent with the ability to understand and comply with the requirements of the study.

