Appendix 4 – PGI

Patient Global Impression of Improvement

Check the one number that best describes how your urinary tract condition is now compared with how it was before you started treatment with the BlueWind RENOVA iStim™ System

1	Very much better
2	Much better
3	A little better
4	No change
5	A little worse
6	Much worse
7	Very much worse

Number	Version / Date	Page
G02-CLP-0002_US	Rev. 08 / 27July 2021	73 of 75

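### BSW item 3 asks about continuing 'this medication' in a device trial that allows OAB drugs, so some willingness answers may not concern the device

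*Protocol*

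**What the plan says.** Protocol Appendix 1 reproduces the BSW form, which the physician administers. It has three items.

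- Item 1 asks about "any benefit from your treatment".
- Item 2 asks "are you satisfied with your treatment".
- Item 3 asks whether the subject would be "willing to continue treatment with this medication". After a yes, the form asks "Would you be a little bit willing to continue treatment with this medication or very willing to continue treatment with this medication". After a no, it asks "Would you be a little bit unwilling to continue treatment with this medication or very unwilling to continue treatment with this medication".

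The study treatment is the RENOVA iStim System, given to every subject in a single arm (Protocol synopsis, Study Arms). OAB drugs are not study treatments, but they are permitted. Under inclusion criterion 7 (Protocol 10.7.1), users of antimuscarinics or beta-3 agonists must have been on a stable dose before baseline and "agree to remain on stable medication consumption until the 12-month follow-up visit". Protocol 10.4.2 records medically required changes of OAB drug and keeps the subject in the study.

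BSW is collected at 6, 12, 24 and 36 months (Protocol 11.4 and the two schedule tables). Protocol 10.3.3 lists it among the other endpoints, which have no formal testing or type I error control. SAP 12.6.3 summarises it descriptively in the ITT, PP and OR1 sets.

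The PGI-I form, collected at the same visits, asks for a comparison with the time "before you started treatment with the BlueWind RENOVA iStim" System (Protocol Appendix 4).

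**The concern.** Item 3 is the only BSW item on willingness to continue, and its object is a medication. The thing the trial wants to know about is a device. A woman taking an antimuscarinic or beta-3 agonist at the visit has a real drug that fits the words. A woman taking none has no OAB drug that fits them and must infer that the device is meant.

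The possible error has no known direction. Inclusion criterion 6 requires an inadequate response to earlier treatment, including drug treatment. A literal no about a drug that has not worked well enough would be recorded as unwillingness to continue with the device. A literal yes about a tolerated drug would be credited to the device. The agreement to keep OAB drugs stable ends at month 12, while BSW continues to month 36, so changes in drug use could also move the willingness result between visits with no change in attitude to the device.

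What is at stake is the interpretation of one descriptive result at four visits.

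**Working it through.** No sample size, power, alpha or performance goal is attached to BSW, so there is no plan figure to reproduce. The check is a comparison of texts.

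1. **How often the phrase occurs.** The lead question uses it once and each of the two follow-ups uses it twice: 1 + 2 + 2 = 5. It is the consistent wording of item 3, not a single stray word.
2. **What it can refer to.** The study treatment is an implant powered by a wearable unit (Protocol 6.2). The OAB medication a subject may be taking is a concomitant drug allowed under Protocol 10.4 and 10.7.1. Read literally, the words fit the drug and not the device.
3. **Whether anything redirects the reader.** Neither the protocol nor the SAP instructs the physician to substitute the device, and the form gives the question as a script to be put to the patient. The SAP has no BSW scoring or interpretation rule.
4. **Comparison with the sister form.** The PGI-I names the device. The two forms are used at the same visits, so the trial already has suitable wording that was not carried over to BSW.
5. **Items 1 and 2.** Both speak of the subject's treatment. That is less specific than the PGI-I, but it is not wrong in a trial where the device is the treatment.
6. **Size.** The share of willingness answers that concern an OAB drug is p × m, where p is the share of subjects on an OAB drug at the visit and m is the share of those who answer about the drug. The documents give neither. The product is 0 if m = 0 and p if m = 1, so the possible range runs from zero to the full share on an OAB drug, with no basis for choosing a point within it.
7. **Whether the data allow a breakdown.** The schedule tables show medications recorded at the 6-, 12-, 24- and 36-month visits, the same visits as BSW. Willingness can therefore be tabulated by OAB drug use without new data collection.

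**The case against.** The strongest reply is that the setting makes the meaning clear. A physician asks the question at a visit where the device is inspected and its settings re-evaluated (Protocol 11.4.5), after two items about the subject's treatment. Most women may well answer about the device. This has force: it means the size could be negligible. It does not remove the point, because nothing secures the clarification, and up to 30 sites could each handle the script differently.

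The stakes are also limited. BSW is one of many descriptive endpoints, the fault is in one of its three items, and compliance and device usage are reported separately. This stands in full.

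The fielded eCRF is not among the documents and may be worded differently. This also stands, and it determines the first step of the fix.

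A reader might infer more than the documents support, in four ways.

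- *That no willingness answer can be attributed to the device.* The text supports only that some answers may concern a drug. Physician administration at device visits makes the blanket statement too strong.
- *That the OAB-medication subgroup analysis in SAP 12.8 is damaged.* That analysis concerns the primary endpoint, a diary measure. BSW is not compared by OAB drug use anywhere in the plan.
- *That a percentage of misdirected answers can be stated.* Any such figure would rest on an assumed misreading rate with no source in the documents.
- *That items 1 and 2 need rewording too.* Their wording is not wrong, and changing it would cost comparability between visits with no error to correct.

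**Conclusion.** The point holds for item 3 and its two follow-ups. As printed in Appendix 1, they ask about a medication in a trial of a device whose subjects may be taking OAB drugs, so the willingness result cannot reliably be attributed to the device. The size is unknown and may be near zero. The primary and secondary conclusions, the sample size and the error control are not touched.

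The conclusion assumes that the form in use matches Appendix 1 and that at least some subjects are on an OAB drug when asked. The correction is still worth making: the endpoint is pre-specified at four visits, item 3 is the only BSW item on willingness, and the change is specific and cheap.

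**What to change.** 1. Check the BSW wording on the fielded eCRF. If it already names the device, correct Appendix 1 to match and stop there.
2. If it matches Appendix 1, replace *this medication* with *the RENOVA iStim System* in item 3 and both follow-ups for remaining visits. Check first for any conditions on modifying the instrument. Leave items 1 and 2 unchanged.
3. For forms already completed, state in the report which wording was used, and show willingness separately for women with and without an OAB drug at that visit, using the medication records already collected.

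**Cost.** A protocol and form amendment submitted to the ethics committees, with approval before use where that applies (Protocol 19); SAP 1.1 lists four country protocols. It makes a small change to a standard instrument. It also leaves two versions of item 3: women already past month 12 would have the old wording at 6 and 12 months and the new wording later, so comparisons of willingness over time need a note on the version used.

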Appendix 2 - MESA incontinence questionnaire

MESA Incontinence Questionnaire

Urge Incontinence Questions

Some people receive very little warning and suddenly find that they are losing, or about to lose, urine beyond their control. How often does this happen to you?				
	_Sometimes (2)			
	t or find a toilet that is	occupied and you	have an urge to urinate, how often do you end	
Do you lose urine when	n vou suddenly have th	e feeling that you	r bladder is full?	
Often (3)				
		-		
Does washing your har Often (3)			Never (a)	
Otten (3)	50111ctimes (2)	Rarciy (1)		
Does cold weather cau	se you to lose urine?			
Often (3)	Sometimes (2)	Rarely (1)	Never (0)	
Does drinking cold bev	verages cause you to los	se urine?		
	Sometimes (2)		_Never (o)	
TOTAL URGE SCORE URGE SCORE RATIO				
Stress Incontinence	e Questions			
Does coughing gently	cause you to lose urine	?		
Often (3)	Sometimes (2)	Rarely (1)	_Never (0)	
Does coughing hard ca	use you to lose urine?			
Often (3)		Rarely (1)	_Never (0)	
-		•		
Does sneezing cause yoOften (3)	ou to lose urine?	Rarely (1)	Never (a)	
Otten (3)	50111ctimes (2)	Rarciy (1)		
Does lifting things cau	se you to lose urine?	5 1 ()	27. ()	
Often (3)	Sometimes (2)	Rarely (1)	Never (0)	
Does bending over cau	se you to lose urine?			
Often (3)	Sometimes (2)	Rarely (1)	_Never (0)	
Does laughing cause yo	ou to logo urino?			
	Sometimes (2)	Rarely (1)	Never (o)	
Does walking briskly c	ause you to lose urine?	Doroly (1)	Novor (o)	
Orten (3)	_Sometimes (2)	Kareiy (1)	never (0)	
Does straining, if you a				
Often (3)	Sometimes (2)	Rarely (1)	Never (o)	

Number	Version / Date	Page
G02-CLP-0002_US	Rev. 08 / 27July 2021	68 of 75

Does getting up from	a sitting to a standing	g position cause yo	ou to lose urine?
Often (3)	Sometimes (2)	Rarely (1)	Never (o)
TOTAL STRESS SCO	RE		
STRESS SCORE RAT			

Add the total score for each category. For urge incontinence, the maximum total score is 18 based on 6 questions, with a maximum score of 3 for each question. For stress incontinence, the maximum score is 27, based on a question with a maximum score of 3 for each question. To determine predominance of either stress or urge incontinence, the percent score is obtained (by dividing the score by the maximum total possible score, e.g., 9 urge score divided by $18 \times 100 = 50\%$ urge vs. 9 stress score divided by $27 \times 100 = 33\%$. Urge is considered predominant when the % score of urge is greater than stress.)

Number	Version / Date	Page
G02-CLP-0002_US	Rev. 08 / 27July 2021	69 of 75

Apı	pen	dix	3 -	OA	B-q
-----	-----	-----	-----	----	-----

Pt Initials:	Pt ID No.:

OAB-q

This questionnaire asks about how much you have been bothered by selected bladder symptoms during the past 4 weeks. Please *check the box* that best describes the extent to which you were bothered by each symptom during the past 4 weeks. There are no right or wrong answers. Please be sure to answer every question.

	ring the past 4 weeks, how bothered re you by	Not at all	A little bit	Some- what	Quite a bit	A great deal	A very great deal
1.	Frequent urination during the daytime hours	1		3		5	6
2.	An uncomfortable urge to urinate			3	4	5	6
3.	A sudden urge to urinate with little or no warning		2	3	4	5	6
4.	Accidental loss of small amounts of urine	1		3	4	5	6
5.	Nighttime urination			3	4	5	6
6.	Waking up at night because you had to urinate		2	3	4	5	6
7.	An uncontrollable urge to urinate			3	4	5	6
8.	Urine loss associated with a strong desire to urinate	1	2	3	4	5	6

The above questions asked about your feelings about individual bladder symptoms. For the following questions, please think about your overall bladder symptoms in the past 4 weeks and how these symptoms have affected your life. Please answer each question about how often you have felt this way to the best of your ability. Please *check the box* that best answers each question.

Number	Version / Date	Page
G02-CLP-0002_US	Rev. 08 / 27July 2021	70 of 75

2

Pt ID No.:____

Pt Initials:

During the past 4 weeks, how often have your bladder symptoms	None of the time	A little of the time	Some of the time	A good bit of the time	Most of the time	All of the time
Made you carefully plan your daily travelling?		2	3	Ģ	5	6
10. Caused you to feel drowsy or sleepy during the day?		2	3	Image: Control of the	5	6
Caused you to plan "escape routes" to toilets in public places?		2	3	Ģ	5	6
12. Caused you distress?		2	3	-	5	6
13. Frustrated you?		2	3	-	5	6
14. Made you feel like there is something wrong with you?		2	3	-	5	6
15. Interfered with your ability to get a good night's rest?		2	3	-	5	6
 Caused you to reduce your physical activities (exercising, sports, etc.)? 		2	3	Image: Control of the	5	6
Prevented you from feeling rested upon waking in the morning?		2	3	-	5	6
18. Frustrated your family and friends?		2	3	-	5	6
19. Caused you anxiety or worry?		2	3	Ģ	5	6
Caused you to stay home more often than you would prefer?		2	3	Ġ	5	6
21. Caused you to adjust your travel plans so that you are always near a toilet?		2	3	ŗ	5	6
22. Made you avoid activities away from toilets (i.e., walks, running, hiking)?		2	3	Ģ	5	6
23. Made you frustrated or annoyed about the amount of time you spend in the toilet?	-	2	3	Ģ	5	6
24. Awakened you during sleep?		2	3	Image: Control of the	5	6
25. Made you worry about odour or hygiene?		2	3	Ō	5	6
26. Made you uncomfortable while travelling with others because of needing to stop to go to the toilet?		2	3	Ċ	5	6

UK OAB-q, ver 1.0, 2004

Number	Version / Date	Page
G02-CLP-0002 US	Rev. 08 / 27July 2021	71 of 75

Pt Initials:				Pt ID No.:		
During the past 4 weeks, how often have your bladder symptoms	None of the time	A little of the time	Some of the time	A good bit of the time	Most of the time	All of the time
27. Affected your relationships with family and friends?		2	3	Ģ	5	6
28. Caused you to reduce participating in social gatherings, such as parties or visits with family or friends?		2	3	Ģ	5	6
29. Caused you embarrassment?		2	3	-	5	6
30. Interfered with getting the amount of sleep you needed?		2	3	Ģ	5	6
31. Caused you to have problems with your partner or spouse?		2	3	-	5	6
32. Caused you to plan activities more carefully?		2	3	ŗ	5	6
33. Caused you to locate the closest toilet as soon as you arrive at a place you have never been?	-	2	3	Ģ	5	6

Number	Version / Date	Page
G02-CLP-0002_US	Rev. 08 / 27July 2021	72 of 75

[©] Copyright 2004 Pfizer. All rights reserved.

Appendix 4 – PGI

Patient Global Impression of Improvement

Check the one number that best describes how your urinary tract condition is now compared with how it was before you started treatment with the BlueWind RENOVA iStim™ System

1	Very much better
2	Much better
3	A little better
4	No change
5	A little worse
6	Much worse
7	Very much worse

Number	Version / Date	Page
G02-CLP-0002_US	Rev. 08 / 27July 2021	73 of 75

Appendix 5 - PHQ-15

PHYSICAL SYMPTOMS (PHQ-15)

During the past 4 weeks, how much have you been bothered by any of the following problems?

	Not bothered at all (0)	Bothered a little (1)	Bothered a lot (2)	
a. Stomach pain				
b. Back pain				
c. Pain in your arms, legs, or joints (knees, hips, etc.)				
d. Menstrual cramps or other problems with your periods WOMEN ONLY				
e. Headaches				
f. Chest pain				
g. Dizziness				
h. Fainting spells				
i. Feeling your heart pound or race				
j. Shortness of breath				
k. Pain or problems during sexual intercourse				
I. Constipation, loose bowels, or diarrhea				
m. Nausea, gas, or indigestion				
n. Feeling tired or having low energy				
o. Trouble sleeping				
(For office coding: Total Score T = +)				

Developed by Drs. Robert L. Spitzer, Janet B.W. Williams, Kurt Kroenke and colleagues, with an educational grant from Pfizer Inc. No permission required to reproduce, translate, display or distribute.

Number	Version / Date	Page
G02-CLP-0002_US	Rev. 08 / 27July 2021	74 of 75

Number	Version / Date	Page
G02-CLP-0002_US	Rev. 08 / 27July 2021	75 of 75

		12.6.1 Primary Efficacy Analysis	
		12.6.2 Secondary Efficacy Analysis	22
		12.6.3 Additional Efficacy Analysis	22
12.7	Sens	itivity Analysis	23
	12.8	Covariate, Subgroup, and 'Poolability' Analyses	23
13	Data	Listings	. 24
14	Com	puter Software	. 25
15	Appe	endix 1: Rules for Correction of Discrepancies in Paper Diaries	. 26
16	Appe	endix 2: Rules for Diary Calculations	. 26

List of Abbreviations

AE	Adverse Event
BSW	Benefit, Satisfaction and willingness to Continue questionnaire
СР	Clinician Programmer
CRF	Case Report Form
CS	Clinically Significant
HRQL	Health Related Quality of Life
ITT	Intent to Treat
MAR	Missing At Random
MESA	Medical, Epidemiological, and Social Aspects of Aging
MI	Multiple Imputation
MID	Minimal Important Difference
OAB	Over Active Bladder
OABq	Over Active Bladder questionnaire
OASIS	Over Active bladder Stimulation System
OR1	One Month Responders
OUS	Outside of United States
PGI-I	Patient Global Impression of Improvement
PHQ-9 (or 15)	Patient Health Questionnaire
PP	Per Protocol
PPIUS	Patient Perception of Intensity of Urgency Scale
QoL	Quality of Life
SAE	Serious Adverse Event
SAP	Statistical Analysis Plan
SUI	Stress Urinary Incontinence
UUI	Urinary Urge Incontinence

1 Introduction

1.1 General

This is a prospective, single arm, multi-center, open label study whose primary objective is to assess the safety and efficacy of the BlueWind RENOVA iStim™ system for the treatment of UUI. The trial's secondary objectives are to evaluate device performance, durability of effect and patient reported outcomes (PROs) such as quality of life (QoL). This SAP is applicable to the following protocol versions:

Country	Document No.	Version/Date
Belgium	G02-CLP-002_BE	Rev. 06 / 27 Jul 2021
Netherlands	G02-CLP-002_NL	Rev. 06 / 27 Jul 2021
United Kingdom	G02-CLP-002_UK	Rev. 06 / 27 Jul 2021
United States	G02-CLP-002_US	Rev. 06 / 27 Jul 2021

Once all patients complete six months of follow-up, a complete data analysis will be performed and submitted to relevant regulatory bodies, with a 12-month update and endpoint evaluation performed and submitted at study completion.

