10.3.2 Secondary Endpoints

Bluewind will test three secondary endpoints. In order to control type I error of the family of secondary objectives at 5%, secondary objective hypothesis testing will only occur upon rejection of the primary objective null hypothesis.

- Proportion of subjects with ≥10 points (MID) improvement in HRQL (based on OAB-q) at 6 months post system activation
- Proportion of responders at 12 months post system activation as demonstrated by ≥50% improvement in either average number of urgency related incontinence episodes or average number of severe/large urgency related incontinence episodes, as measured by 7-day Patient Voiding Diary.

Number	Revision / Date	Page
G02-CLP-0002_US	Rev. 08 / 27 July 2021	30 of 75

 Proportion of responders at 6 months post system activation as demonstrated by ≥50% improvement in the average number of moderate-severe urgency episodes PPIUS degree 3,4 or <8 voids/day

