according to EU GDPR guidelines effective as of 25- May- 2018. All reports and communications relating to subjects in the study will identify the subjects by their subject ID number only.

21. Termination of the Clinical Study

The sponsor will notify the involved ethics committees and the competent authorities of the end of the study within a period of 90 days or per the EC requirements, whichever is sooner. The end of the study is defined as the last patient's last visit.

In case the study is ended prematurely, the sponsor will notify the responsible ECs and the competent authorities within 15 days, including the reasons for the premature termination.

At the completion of the last follow-up visit, patient will exit the study. However, the implant will not be explanted and the patient will be clinically followed up per physician discretion. System support will be provided by BlueWind Medical for 3 years post activation.

22. Insurance

Study subject insurance coverage will be provided according to the laws of the country where the study will be conducted.

In Europe, the insurance company is Newline Syndicate 1218 at Lloyd's and in the US, the insurance company is Medmarc Insurance Group.

23. Publication Policy

It is BlueWind Medical's policy to publish the results of its Clinical Trials.

The publication of the common database will be under the direction of the study manager. Publication of the complete data set will not be allowed unless approved by the study manager.

Individual investigators may publish their own data based on the terms and conditions specified in the clinical trial agreement.

All publications will be reviewed by BlueWind Medical in order to assure that no confidential information is disclosed. Such confidential information is not allowed for publishing.

A final study report will be submitted, including any publications/abstracts of the study, to the accredited EC/IRB and the Competent Authority within one year after the end of the study.

24. Reporting Results on ClinicalTrials.gov

The clinical investigation will be registered on ClinicalTrials.gov. A full report of the pre-specified outcomes, regardless of the results, will be made public through the ClinicalTrials.gov website no later than 12 months after clinical investigation completion, as required by section 801 of the Food and Drug Administration (FDA)

Number	Revision / Date	Page
G02-CLP-0002_US	Rev. 08 / 27 July 2021	63 of 75

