12.6.2.1 Multiple Comparisons for Secondary Analyses

The secondary hypotheses will be tested only if the null primary is rejected.

The secondary endpoints will be tested using Hochberg step-up procedure to control the overall type I error rate.

The calculation of each comparison to performance goal will be performed separately rather than simultaneously, as done in the Hochberg procedure. In addition, each hypothesis will be tested with two-sided (unadjusted) Alpha = 0.05.

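### The secondary Hochberg family includes a 12-month endpoint, but SAP 1.1 submits a complete analysis at 6 months, so the 6-month secondary claims cannot always be decided by the stated step-up

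*SAP*

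**What the plan says.** SAP 12.6.2 lists three secondary endpoints with performance goals: HRQL improvement at 6 months (50%), leaks or large leaks at 12 months (50%), and urgency episodes or voids at 6 months (45%). It declares each a success when its own lower confidence bound exceeds its goal, and states no adjusted level.

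SAP 12.6.2.1 sets a gate, "The secondary hypotheses will be tested only if the null primary is rejected", and then a method: "The secondary endpoints will be tested using Hochberg step-up procedure to control the overall type I error rate". It goes on: "The calculation of each comparison to performance goal will be performed separately rather than simultaneously, as done in the Hochberg procedure", and adds that "each hypothesis will be tested with two-sided (unadjusted) Alpha = 0.05". Protocol 10.3.2 gives the aim: "In order to control type I error of the family of secondary objectives at 5" per cent.

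On timing, SAP 1.1 says: "Once all patients complete six months of follow-up, a complete data analysis will be performed and submitted to relevant regulatory bodies". The 12-month endpoint follows, "with a 12-month update and endpoint evaluation performed and submitted at study completion". Neither section states a waiting rule, reserved alpha, testing order or provisional status for the 6-month secondary results.

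**The concern.** A step-up starts from the largest p-value in the family. Here one of the three p-values becomes available at least six months after the other two have been analysed and submitted. The analyst at 6 months must either hold back some results, test a reduced family, or fall back on the separate unadjusted tests. The documents do not choose between the first two, and the third abandons the error control that both documents promise.

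The urgency endpoint is one of the two affected at 6 months, and it is the endpoint that sets the total of 150 subjects. At stake is whether a secondary claim sent to regulators is valid under the stated family error, and whether it could later have to be withdrawn.

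**Working it through.** **1. The plan's own figure.** SAP section 9 gives 61% against 45%, one-sided 0.025, exact binomial, power at least 85%. With n = 89, success needs at least 50 responders: P(X ≥ 50 | 0.45) = 0.0223 and P(X ≥ 50 | 0.61) = 0.851. Then 89/0.85 = 104.7, rounded up to 105, and 105/0.70 = 150. The plan's figures reproduce.

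**2. What can be decided at 6 months.** With three endpoints at two-sided 0.05, the thresholds are 0.05 (largest p), 0.025 (middle) and 0.05/3 = 0.0167 (smallest). Hochberg is monotone in its p-values, so setting the 12-month p to 1 and then to 0 brackets every possible outcome.

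- 12-month p = 1: both 6-month endpoints are rejected if the larger p ≤ 0.025; otherwise the smaller is rejected if ≤ 0.0167.
- 12-month p = 0: both are rejected if the larger p ≤ 0.05; otherwise the smaller is rejected if ≤ 0.025.

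A claim is open when the two cases differ.

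| 6-month p-values | 12-month p | Rejected at 6 months by the three-member step-up |
|---|---|---|
| 0.012, 0.024 | 0.90 | both (final whatever the 12-month p) |
| 0.02, 0.04 | 0.03 | both |
| 0.02, 0.04 | 0.20 | neither |

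**3. How often a claim is open.** On the one-sided scale the thresholds halve to 0.025, 0.0125 and 0.0083. Inputs: urgency n = 89 and rate 61% (SAP section 9). Assumed, because the documents give no planning values: HRQL n = 128 (150 × 0.85, rounded) and rate 65%. Exact binomial probabilities:

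- Urgency: P(p ≤ 0.025) = 0.8509; P(p ≤ 0.0125) = 0.7294.
- HRQL: P(p ≤ 0.025) = 0.9220; P(p ≤ 0.0125) = 0.8544; P(0.0083 < p ≤ 0.0125) = 0.0457.

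Under independence:

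- Both ≤ 0.025 but not both ≤ 0.0125: 0.9220 × 0.8509 − 0.8544 × 0.7294 = 0.161.
- HRQL in 0.0083-0.0125 with urgency above 0.025: 0.0457 × (1 − 0.8509) = 0.007. The mirror case is zero, because no urgency count gives a p in that band.
- Total: 0.168.

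Simulation gives 0.153 at correlation 0.5, and about 0.127 with HRQL at 70%. The range is therefore 13-17% with urgency at 61%, and 12-19% over all scenarios run (HRQL 58-70%, urgency 53-61%).

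**4. Family error.** Claims are made only in the favourable direction, so two-sided 0.05 means 0.025 per test. The figures below assume that the primary gate is passed and that all three secondary nulls are true.

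| Procedure | One-sided family error |
|---|---|
| Full three-member Hochberg | 2.5% independent; 2.3% at correlation 0.5 |
| Separate unadjusted tests | 1 − 0.975³ = 7.3% independent; 6.3% at correlation 0.5 |
| Two-member Hochberg at 6 months, 12-month endpoint later at full alpha | 1 − 0.975² = 4.9% independent; 4.2% at correlation 0.6 |

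The last row is one way an analyst might fill the gap. The SAP does not prescribe it.

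**5. Reversal.** Suppose a two-member Hochberg is used at 6 months and the full step-up is run later, with urgency at 61% and an assumed n = 128 at 12 months. The chance that a submitted claim is lost is 1-2% if the 12-month rate is 65% (HRQL 65-70%). With HRQL at 65% it is 14% if the 12-month rate is 55%, and 15-17% if it is 50%.

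**The case against.** The strongest reply is that SAP 12.6.2.1 does cover the interval: each comparison is made separately, so each endpoint is judged when its data arrive. That is a fair literal reading. But it contradicts the Hochberg sentence in the same subsection and gives up the family control in Protocol 10.3.2, so it does not rescue the plan.

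Four stronger readings are tempting, and the documents do not support them.

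- *The 6-month claims cannot be decided at all.* They often can. With urgency at its planned rate, nothing is left open in about 83-87% of trials.
- *There is a 12% chance of losing the urgency claim.* The figure 0.8509 − 0.7294 = 0.1215 is only the chance that the urgency p falls between one-sided 0.0125 and 0.025. A loss also needs HRQL to pass and the 12-month endpoint to miss. The 12-month endpoint is an either/or composite, so its rate cannot be below the leak-only rate at 12 months. A rate of 50-55% would therefore mean that the effect seen in the primary planning rate of 65% had faded.
- *The plan's error rate is 4.9%.* That figure belongs to a procedure the SAP does not state. It also presumes that the primary gate is passed, all three secondary nulls are true and the endpoints are independent. If the primary null were itself true, the gate would hold the error far lower.
- *The 12-month evaluation waits until 36 months.* Protocol section 21 supports this: "The end of the study is defined as the last" patient's last visit, and follow-up runs to 36 months. But SAP 1.1 calls it a 12-month update, the visit schedule puts a completion form at 12 months, and the protocol describes subjects who completed 12 months and exited. The wording is ambiguous.

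**Conclusion.** The point holds in a limited form. One Hochberg family spans two analysis times, and the plan has no valid rule for the first. At least one 6-month claim stays open in about 13-17% of trials, with urgency at its planned 61% and HRQL at an assumed 65-70%. The only text that permits a 6-month decision gives about 7.3% one-sided family error under independence against 2.5%, under the conditions stated in the working.

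If the gap were filled by a two-member Hochberg, error would be about 4.2-4.9%. Reversal of a submitted claim would range from 1-2% to 14-17%, depending on an assumed 12-month rate of 65% or 50-55%.

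These figures use exact binomial p-values in place of the SAP's multiple-imputation logistic test. The primary endpoint is tested first, at 6 months, and is unaffected. No change in sample size follows. This should be corrected because following the SAP as written can produce a secondary claim without the promised error control.

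**What to change.** In SAP 12.6.2.1, delete the two sentences on separate and unadjusted testing and insert:

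*At the 6-month analysis the p-value of the 12-month endpoint is set to 1. Both 6-month endpoints are claimed if the larger two-sided p-value is at most 0.025; otherwise the one with the smaller p-value is claimed if it is at most 0.0167. The step-up is completed once all subjects have passed the 12-month visit, which can only add claims.*

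In SAP 12.6.2, make the confidence-bound criterion subject to this rule. In SAP 1.1, replace the reference to study completion with the date on which all subjects have passed the 12-month visit.

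The final Hochberg is unchanged. Simulated family error over both stages is 0.025 under independence and 0.023 at correlation 0.5, and no early claim can be withdrawn.

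The cost is that a borderline 6-month result waits. Power to claim the urgency endpoint at the 6-month submission is about 73%, against about 83% in the final step-up with HRQL and the 12-month endpoint both at 65%. If the 12-month rate is 55%, the final figure is itself only 74-75%, so little is lost by early testing.

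If the sponsor values the 6-month claims more, an alternative is to run Hochberg on the 6-month pair at full alpha and test the 12-month endpoint only if both are rejected. Simulated error is 0.024-0.025 and urgency power is 0.84. Power for the 12-month endpoint falls to 0.72-0.77, from 0.89-0.91 in the step-up (HRQL and 12-month rates both 65%). This replaces the stated procedure rather than completing it.
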